2.9.2 Deaths

A separate summary of adverse events causing death will be presented by treatment group.

2.9.3 Liver Safety

A summary of liver events will be presented by treatment group.

2.9.4 Renal Safety

A summary of renal events will be presented by treatment group.

2.9.5 Laboratory data

The summary of laboratory evaluations will be presented for 3 groups of laboratory tests (hematology, serum chemistry and urinalysis). For urinalysis, frequency tables will be presented. Descriptive summary statistics for the change from baseline to each study visit will be presented. These descriptive summaries will be presented by visit, laboratory test and study treatment group. Change from baseline will only be summarized for patients with both baseline and post baseline data. For each parameter, the maximum change (maximum decrease and maximum increase) from baseline within each study period will be evaluated analogously.

In addition, shift tables will be provided for all parameters to compare a patient's baseline laboratory evaluation relative to the visit's observed value. For the shift tables, the normal laboratory ranges will be used to evaluate whether a particular laboratory test value was normal, low, or high for each visit value relative to whether or not the baseline value was normal, low, or high.

These summaries will be presented by laboratory test and study treatment group. Shifts will be presented by visit as well as for most extreme values post-baseline.

Individual subject data listings will be provided for subjects with abnormal laboratory data.

Box plots may be presented for selected laboratory parameters (WBC, neutrophils (absolute count), AST, ALT and creatinine). These box plots would show the following location parameters: The bottom and top edges of the box will represent the 25th and 75th percentile, respectively. The center horizontal line of the box will represent the median. Lower and upper whiskers will reach to the 10th and 90th percentile, respectively. Values below the 10th percentile and above the 90th percentile will be presented by circles. Mean values will also be represented in the plot and connected with a line.

2.9.6 Other safety data

2.9.6.1 ECG and cardiac imaging data

Not applicable

2.9.6.2 Immunogenicity

Summary statistics will be provided for the percentage of patients with blood samples for immunogenicity (anti-AIN457 antibodies).

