1.2.2.2 Other secondary objectives

- To evaluate the therapeutic effect of secukinumab versus placebo on joint synovitis from Baseline to Week 8 using the GLOESS score out of 48 joints

- To evaluate the therapeutic effect of secukinumab versus placebo on enthesitis at Week 12 using the OMERACT enthesitis score for each affected enthesis
- To evaluate the overall safety, tolerability and immunogenicity of secukinumab.

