2.1 Data analysis general information

The analysis outlined in this document will be performed by Novartis using SAS version 9.3 or higher software. All analyses outlined will also be performed by Novartis.

Comparative efficacy analyses (i.e. inferential efficacy comparisons with placebo) will focus on the time period when both active drug and the placebo are given in a manner suitable for making comparisons (e.g. double-blind). For AIN457F2354 this is the first 12-weeks of treatment. Comparative efficacy will be performed based on the FAS population using the randomized treatment. After week 12, the active secukinumab regimens will be compared using confidence intervals on the FAS population using treatment sequence. These treatment sequences represent the treatment combinations the subjects experience over the course of the entire trial in case of treatment switch at week 12.

The Week 3 efficacy assessment was removed from the study assessments in Protocol Amendment 2. Statistical comparisons at week 3 will not be presented due to the low number of subjects enrolled prior to this amendment.

Summary statistics for continuous variables will include N, mean, standard deviation, minimum, lower quartile, median, upper quartile and maximum values. Summary statistics for binary or discrete variables will be presented in contingency tables and will include absolute and relative frequencies.

The statistical analysis planned for the primary and secondary objectives are clearly stated, if not otherwise specified 95% confidence intervals may be presented along with point estimates and p-values will be presented as 1-sided.

Data analyses and summaries will be performed by treatment group (Secukinumab 150mg + 300 mg and Placebo) for baseline measurements, efficacy and safety data captured within the placebo-controlled period and for adverse events throughout the treatment periods.

Analyses of all efficacy and non-AE safety parameters for the treatment periods will be performed by treatment sequence and results presented for the following groups: secukinumab (150 mg + 300 mg), placebo – secukinumab (150 mg + 300 mg).

All listings will be presented by treatment sequence for efficacy and non-AE safety and by treatment for baseline and AE listings.

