2.9.6.7 Antibodies

A listing of the anti-CCP antibodies, Rheumatoid Factor (RF), Antinuclear antibodies (ANA) and anti-dsDNA antibodies will also be listed by visit and treatment group.

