2.10 Pharmacokinetic endpoints

All patients with concentration data will be included in the pharmacokinetic data analysis.

The following pharmacokinetic parameter will be determined: Cmin,ss. Cmin,ss will be determined using Phoenix software. Individual serum concentrations in $\mu\text{g}/\text{ml}$ will be listed. All concentrations below the limit of quantification or missing data will be labeled as such in the concentration data listings. Concentrations below the limit of quantification will be treated as zero in summary statistics for concentration data only. During modeling of the pharmacokinetics of secukinumab, the broad principles outlined in the FDA Guidance for Industry: Population Pharmacokinetics will be followed.

Summary statistics by visit/time will be provided for the above mentioned parameters and will include arithmetic and geometric means, SD, median, minimum and maximum. Individual concentrations will be listed by patient.

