2.13 Biomarkers

Not applicable.

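### Section 2.9.6.2 summarises how many patients have immunogenicity blood samples, not how many test positive for anti-AIN457 antibodies, so as written it does not answer the immunogenicity part of the secondary objective

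*SAP*

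**What the plan says.** Section 1.2.2.2 of the SAP lists among the other secondary objectives: "To evaluate the overall safety, tolerability and immunogenicity of secukinumab".

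Section 2.9.6.2 (Immunogenicity) consists of one sentence and shows no redaction: "Summary statistics will be provided for the percentage of patients with blood samples for immunogenicity (anti-AIN457 antibodies".

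Two general rules bear on any antibody table. Section 2.1 sets the grouping: "Analyses of all efficacy and non-AE safety parameters for the treatment periods will be performed by treatment sequence". Section 2.1.1 takes the last assessment before the first dose of study treatment as the safety baseline, and allows only one baseline per patient, tied to the first randomization. Under section 1.1, placebo patients start open-label secukinumab at Week 12.

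**The concern.** The objective asks about an immune response to the drug. The planned statistic has patients with a sample as its numerator, so it describes how complete the blood draws were. A programmer who follows the sentence produces a correct table of the wrong quantity.

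At stake is whether the planned output answers the immunogenicity part of one secondary objective. Without a stated numerator and denominator, any antibody rate in the study report would have to be defined outside the plan. That includes the choice of how to treat patients already positive before treatment.

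**Working it through.** The SAP states no immunogenicity figure, so there is nothing to reproduce. The check is mainly textual.

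**Step 1: what the sentence computes.** Planned statistic = patients with an immunogenicity sample / patients. Statistic the objective needs = patients positive for anti-AIN457 antibodies / patients with an evaluable sample. The number of positive patients does not appear in the first ratio, so that ratio cannot respond to it.

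**Step 2: whether another section supplies the missing count.**

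| SAP section | Content | Gives an anti-AIN457 positive count? |
|---|---|---|
| 2.9.6.7 Antibodies | Autoantibody listing: "A listing of the anti-CCP antibodies, Rheumatoid Factor (RF), Antinuclear antibodies (ANA) and anti-dsDNA antibodies will also be listed by visit and treatment group" | No; autoantibodies only |
| 2.9.5 Laboratory data | "The summary of laboratory evaluations will be presented for 3 groups of laboratory tests (hematology, serum chemistry and urinalysis" | No |
| 2.10 Pharmacokinetic endpoints | "The following pharmacokinetic parameter will be determined: Cmin,ss" | No; nothing by antibody status |
| 2.11 PD and PK/PD | Declared not to apply | No |
| 2.13 Biomarkers | "Not applicable" | No |
| 2.9.1.1 Events of special interest | Includes hypersensitivity | No; a clinical event, not an antibody result |
| 2.1 General information | "All listings will be presented by treatment sequence for efficacy and non-AE safety and by treatment for baseline and AE listings" | No; groups listings, creates none |
| 4 Changes to protocol-specified analyses | Nothing on immunogenicity | No |

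**Step 3: illustration of the difference.** The figures in this step are assumptions, except the target of 164 patients (sections 1.1 and 3.1).

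- Sampling: if 156 of 164 patients had a sample, the planned table would show 156/164 = 95.1%, whether none or 10% of them tested positive.
- Incidence: with 0 positives among n evaluable exposed patients, the estimate is 0% and the two-sided exact 95% upper limit is 1 − 0.025^(1/n).
  - n = 120: 1 − 0.025^(1/120) = 3.0%
  - n = 150: 1 − 0.025^(1/150) = 2.4%
  - n = 164: 1 − 0.025^(1/164) = 2.2%

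For comparison, the one-sided 95% bound at n = 150 is 1 − 0.05^(1/150) = 2.0%. The plan should therefore say which interval it means.

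**The case against.** The strongest reply is that this is loose drafting and not a choice of statistic. The section is headed Immunogenicity and the bracket names the antibody, so the natural intent is the percentage of patients whose samples contain anti-AIN457 antibodies. That is probably right, but the text does not say it. The SAP is what gets programmed, so the slip still needs correcting.

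A second reply is that general rules already cover part of the detail: the safety set in section 2.9, the single baseline in 2.1.1, treatment sequence in 2.1, and worst-record selection for categorical safety data in 5.4. This stands as far as it goes. Section 2.1 contains no error and supplies the grouping. None of these rules creates a count of positive patients.

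A third reply is that sampling times, assay and the definition of a positive result commonly sit in the protocol, which is not shown. This also stands, and their absence is not part of the finding. A split between baseline and later positives and an exact interval are good practice in the correction; leaving them out is not a contradiction within the SAP. The finding rests only on the statistic that the SAP does state.

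**Conclusion.** The point holds. As written, section 2.9.6.2 yields a sampling-completeness rate, and no other visible text gives an antibody-positive rate, so the immunogenicity part of the objective in 1.2.2.2 is not answered by the planned output. The consequence is limited: it concerns one descriptive safety summary, and H1 to H4, error control and sample size are unaffected.

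A reader might infer more than this, in three ways:

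- **The trial cannot answer the objective at all.** The documents do not support this. The defect lies in one sentence, and antibody results may well exist.
- **The table will come out near 100%.** That assumes near-complete sampling, which the SAP does not state.
- **Readers will mistake the figure for an incidence.** This is conjecture.

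The conclusion assumes that the redacted parts of the SAP (mainly section 2.8) hold no immunogenicity analysis. Section 2.9.6.2 itself shows no redaction.

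**What to change.** Reword section 2.9.6.2 along these lines:

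- Report the number and percentage of patients testing positive for anti-AIN457 antibodies, with patients who have an evaluable sample as the denominator. Keep the number sampled as the denominator row.
- Show patients positive at baseline, as defined in section 2.1.1, separately from secukinumab-exposed patients who are negative at baseline and positive later. Give a two-sided exact 95% confidence interval for the latter.
- For placebo–secukinumab patients, use a reference sample taken before the first secukinumab dose only if the sampling schedule (not shown) provides one. State this as an explicit exception to the single-baseline rule in section 2.1.1; otherwise the new text would contradict that rule.

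The cost is a few sentences of SAP wording and one table, on the assumption that the existing samples are assayed as planned.

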2.9.6.3 Pregnancy tests

Serum and urine pregnancy tests will be summarized and listed, where applicable.

2.9.6.4 QuantiFERON TB-Gold test

A listing of the QuantiFERON TB-Gold test results will be presented by treatment group.

2.9.6.5 PPD skin test

A listing of the PPD skin test results will be presented by treatment group.

2.9.6.6 Local tolerability (injection site reactions)

A separate summary of injection site reactions will be presented by treatment group.

2.9.6.7 Antibodies

A listing of the anti-CCP antibodies, Rheumatoid Factor (RF), Antinuclear antibodies (ANA) and anti-dsDNA antibodies will also be listed by visit and treatment group.

2.9.6.8 Chest X-ray/MRI

A listing of the chest X-ray/MRI results will be presented by treatment group.

2.9.7 Additional parameters

2.9.7.1 Physical examination

Not applicable.

2.9.7.2 Vital signs

Analysis of vital sign measurements (systolic blood pressure (mmHg), diastolic blood pressure (mmHg) and pulse (bpm)) using descriptive summary statistics for the change from baseline for each post-baseline visit will be performed by vital sign and treatment group. Change from baseline will only be summarized for subjects with both baseline and post-baseline values and will be calculated as:

$$\text{change from baseline} = \text{post-baseline value} - \text{baseline value}$$

The number and percentage of subjects with newly occurring notable vital signs will be presented, by treatment period. Criteria for notable vital sign abnormalities are provided in Table 2 below.

Table 3: Criteria for notable vital sign abnormalities

Vital sign (unit)	Notable abnormalities
Systolic blood pressure (mmHg)	≥ 140 mmHg or < 90 mmHg
Diastolic blood pressure (mmHg)	≥ 90 mmHg or < 60 mmHg
Pulse (bpm)	> 100 bpm or < 60 bpm

A blood pressure indicative of prehypertension (systolic 120 to < 140 mmHg and/or diastolic 80 to < 90 mmHg) will not be regarded as notable.

2.10 Pharmacokinetic endpoints

All patients with concentration data will be included in the pharmacokinetic data analysis.

The following pharmacokinetic parameter will be determined: Cmin,ss. Cmin,ss will be determined using Phoenix software. Individual serum concentrations in $\mu\text{g}/\text{ml}$ will be listed. All concentrations below the limit of quantification or missing data will be labeled as such in the concentration data listings. Concentrations below the limit of quantification will be treated as zero in summary statistics for concentration data only. During modeling of the pharmacokinetics of secukinumab, the broad principles outlined in the FDA Guidance for Industry: Population Pharmacokinetics will be followed.

Summary statistics by visit/time will be provided for the above mentioned parameters and will include arithmetic and geometric means, SD, median, minimum and maximum. Individual concentrations will be listed by patient.

2.11 PD and PK/PD analyses

Not applicable

2.12 Patient-reported outcomes

Not applicable

2.13 Biomarkers

Not applicable.

2.15 Interim analysis

Prior to the Week 52 database lock and end of study reporting there are 3 other analyses planned: a blinded sample size re-estimation (SSR), a Week 12 and a Week 24 analysis.

Blinded Sample Size Re-estimation (SSR)

The blinded SSR will be performed when the first 60 patients have completed the Week 12 visit. The pooled standard deviation of the change from baseline in GLOESS at Week 12 will be calculated for the 60 patients and the pooled change will be transformed based on the placebo response observed in the FUTURE 2 study (CAIN457F2312), roughly 50% of secukinumab. These estimates will be used to decide whether the study should continue as planned.

Although the study is originally designed to have at least 90% power, any change in sample size will be based on 80% power due to enrolment feasibility.

Week 12 analysis

The analysis of the primary and secondary efficacy variables will be performed after all patients complete the Week 12 visit. This analysis will also include exploratory variables outlined up to Week 12 and all available safety data.

Week 24 analysis

The analysis of the exploratory variables up to Week 24 will be performed after all patients complete the Week 24 visit. This analysis will also include all available safety data.

3 Sample size calculation

3.1 Determination of sample size

This study was designed using data for abatacept in the APPRAISE study (RA study to assess early response to abatacept + MTX ([D'Agostino et al, 2016](#)), to test the superiority of secukinumab compared to placebo at the 5% significance level using a 2-sided test. Assuming a difference in the mean change from Baseline at Week 12 in OMERACT global PDUS score of -5.8 with a pooled standard deviation of 13.2, 218 patients in total (109 patients per arm) were estimated to achieve a power of 90% ([EAST 6](#)).

A blinded SSR was performed once the first 60 patients completed the Week 12 visit to evaluate the assumptions used in the sample size calculations. The statistical test for the primary endpoint has been changed from a 2-sided to a 1-sided test.

The first 60 patients to reach Week 12 have a pooled mean change from Baseline at Week 12 in OMERACT global PDUS score of -5.25 with a pooled standard deviation of 9.527. Using the estimated placebo effect of roughly 50% of secukinumab based on data from the FUTURE 2 study (CAIN457F2312) as in the original sample size calculation, the pooled PDUS score change of -5.25 translates to an assumed change of -7.000 and -3.500 for the secukinumab and placebo group, respectively, providing a difference of 3.500 between the groups. Adapting the original sample size calculation to be 1-sided with the power relaxed to 80%, 184 patients in total (92 patients per arm) are required ([EAST 6](#)).

At the time of the blinded sample size calculation, 72 patients were available who had reached their Week 12 visit, to provide the most accurate estimation, all data available were considered i.e. the first 72 patients as opposed to the first 60 patients. Using all available data a difference in the mean change from Baseline at Week 12 in OMERACT global PDUSscore of 4.352 was observed with a pooled standard deviation of 9.822. At the 5% significance level using a 1sided test, 126 patients are needed to achieve a power of 80% ([EAST 6](#)).

The 2 calculations produce a sample size range of 127-185 patients; thus, the sample size will be adjusted to a new target of 164 patients in total (82 patients per arm). This is mid-

way point of the range plus a 5% adjustment based on the observed drop-out rate of patients prior to Week 12 observed at the time of this calculation.

For the secondary variables:

Patients who were naive to TNF α inhibitors were pooled from the 2 confirmatory studies in PsA for secukinumab (CAIN457F2306 and CAIN457F2312) and a placebo response rate of about 29.6% and 10.7% at Week 12 was observed for ACR 20 and ACR 50 respectively. From the same studies pooled, the response rate to secukinumab 150 mg s.c. was around 63.5% (ACR 20) and 33.3% (ACR 50), and the response rate to secukinumab 300 mg s.c. was around 67.2% (ACR 20) and 37.3% (ACR 50). Taking a conservative approach due to the pooled groups, the lowest response rate between the secukinumab arms (i.e. ACR 20 = 63.5% and ACR 50 = 33.3%) was used to estimate the secukinumab response, which resulted in the study having greater than 90% power to detect a difference to placebo using the current sample size.

It is not possible to calculate the power for the SPARCC or early therapeutic effect on affected enthesitis variables due to lack of data available.

4 Change to protocol specified analyses

- The secondary endpoint Change in OMERACT enthesitis score from Baseline to Week 8 for each of the 5 targeted entheses will be updated to change to week 12 to align with the secondary objective “To evaluate the therapeutic effect of secukinumab versus placebo on enthesitis at Week 12 using the OMERACT enthesitis score for each affected enthesis”
- PASI 100 will be summarised alongside PASI 75 and PASI 90.
- ACR 20, ACR 50 and ACR 70 will also be analysed at each timepoint until the end of study [REDACTED] along with Risk Ratios
- Week 12 interim analysis will be known as primary analysis.
- All screened patients analysis set added for disposition summary.

- Non-biologic prior and concomitant medications such as NSAIDs, MTX, Corticosteroids will be classified according to a coding file provided by the medical lead.
- Rules for deriving synovitis composite score were refined to include all permutations of the component data.
- The scoring of PDUS Enthesitis has been updated due to recently published findings that highlight the differences related to B Mode and Doppler. Different scenarios must be explored to develop a global OMERACT enthesitis score at the patient level.

- Non responder imputation (NRI) will be extended up to Week 52 for ACR 20/50/70 & PASI 75/90/100 as supportive analysis to determine the robustness of the data. NRI will also be conducted on the following clinical outcomes;

-
-
- Proportion of patients with a presence of PDUS synovitis (Composite PDUS, SH and PD) will be summarised over time.
-

5 Appendix

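### Does the re-estimated target of 164 patients break the SAP's own 80% power basis for the primary endpoint?

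*SAP*

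**What the plan says.** Section 2.15 sets out the blinded re-estimation. On the data: "The pooled standard deviation of the change from baseline in GLOESS at Week 12 will be calculated for the 60 patients". On the power: "any change in sample size will be based on 80% power due to enrolment feasibility". It adds that the pooled change is to be converted using a placebo response of roughly half that of secukinumab, and that the estimates serve to decide whether the study continues as planned.

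Section 3.1 reports what was done. For the first 60 patients, "the pooled PDUS score change of -5.25 translates to an assumed change of -7.000 and -3.500 for the secukinumab and placebo group, respectively", a difference of 3.500 with SD 9.527; at one-sided 5% and 80% power, "184 patients in total (92 patients per arm) are required". By then 72 patients had reached Week 12 and, "to provide the most accurate estimation, all data available were considered i.e. the first 72 patients as opposed to the first 60 patients". For these, a difference "of 4.352 was observed with a pooled standard deviation of 9.822", giving 126 patients at the same level and power. The two results are given as a range of 127-185, and the section concludes: "thus, the sample size will be adjusted to a new target of 164 patients in total (82 patients per arm"). The target of 164 is the midpoint, "plus a 5% adjustment based on the observed drop-out rate of patients prior to Week 12". The only power stated for the current size is more than 90% for ACR 20 and ACR 50.

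**The concern.** Read together, Sections 2.15 and 3.1 suggest that the trial was to be resized at 80% power on the first 60 patients, that this required 184, and that 164 was adopted instead. A midpoint between two sample sizes is not a power calculation under either set of inputs, and Section 3.1 does not say what 164 delivers for H1. H1 matters most because ACR 20, ACR 50 and SPARCC are tested only if it is rejected. A reader could assume that 164 gives 80% for H1 under the 60-patient estimate, and unadjusted it does not.

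The second worry is the word used for 4.352. A blinded calculation yields a pooled mean, not a difference between arms. The 60-patient changes are correctly described as assumed, but the 72-patient difference is called observed, with neither its pooled mean nor the placebo ratio shown. Taken literally, that would mean arm-level data were seen during the re-estimation. It also concerns the figure that lowers the target below 184.

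**Working it through.** **Inputs (Section 3.1).** 60-patient estimate: difference 3.500, SD 9.527. 72-patient estimate: difference 4.352, SD 9.822. One-sided 5%, 80% power, 1:1 allocation, 5% dropout, 164 randomized.

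**Reproducing the plan's figures.** Total N = 4 × ((1.645 + 0.842) × SD / difference)².

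- 60 patients: 183.2, so 184, as stated.
- 72 patients: 125.97, so 126, as stated.
- The t-test correction adds about 1.645²/2 = 1.35 to each total, giving 184.6 and 127.3. That explains the range of 127-185.
- Midpoint (127 + 185)/2 = 156; 156 × 1.05 = 163.8, so 164, as stated.

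There is no arithmetic error.

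**Power for H1 at 164.** Evaluable per arm: 82 with no loss, or 164 × 0.95 / 2 = 77.9, about 78, with 5% loss. Power = Φ(difference / (SD × √(2/n)) − 1.645).

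| Estimate | n = 78 per arm | n = 82 per arm |
|---|---|---|
| 3.500 / 9.527 | Φ(2.294 − 1.645) = 74.2% | Φ(2.352 − 1.645) = 76.0% |
| 4.352 / 9.822 | Φ(2.767 − 1.645) = 86.9% | Φ(2.837 − 1.645) = 88.3% |

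A blinded SD contains part of the arm difference. Removing it by √(SD² − difference²/4) gives SDs of 9.365 and 9.578. Power is then 75.5-77.3% and 88.4-89.7%, so the picture is the same.

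As an illustration only, averaging the two sets of inputs (difference 3.926, SD 9.675) gives about 81% at 78 per arm and 83% at 82. The compromise therefore sits close to the 80% at which both calculations were run.

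**What the planned model could add.** These are unadjusted two-sample figures. Section 2.5.2 specifies a repeated-measures model with baseline GLOESS and weight as covariates. If the covariates correlate ρ with change, the variance falls by the factor 1 − ρ². Under the 60-patient estimate, 80% is reached when ρ² = 1 − 164/183.23 = 0.105 (ρ = 0.32) with no loss, or 1 − 156/183.23 = 0.149 (ρ = 0.39) with 5% loss. With SD 9.365 the values are 0.27 and 0.34. The SAP gives no correlation, so adjusted power cannot be computed. The 78-per-arm case is also pessimistic, because Section 2.5.3 removes only patients with no post-baseline value.

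**Can 4.352 come from blinded data?** Assume the same placebo ratio of one half. If the secukinumab change is s, the pooled mean is 0.75s and the difference is 0.5s, so the pooled mean is 1.5 times the difference. For the 60 patients, 1.5 × 3.500 = 5.25, as stated. For the 72, 1.5 × 4.352 = 6.528, a pooled mean of −6.528. The 12 added patients would then average (72 × −6.528 + 60 × 5.25)/12 = −12.9.

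For their spread, the total sum of squares is 71 × 9.822² = 6849, of which 59 × 9.527² = 5355 lies within the first 60 and about 588 between the two groups. That leaves about 906 on 11 degrees of freedom, an SD of about 9.1. The mean shift is large, but the figures are compatible with both stated SDs. This shows that a blinded origin is possible; it does not prove it.

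**The case for a change.** The strongest case for a change is that Section 2.15 names the 60 patients and 80% power, that Section 3.1 calls the resulting 184 required, and that the adopted 164 gives roughly 74-76% on those inputs without saying so. Section 2.15 was not brought into line with the 72-patient step. The input that takes the requirement from 184 to 126 is shown without its derivation and under a word that does not fit a blinded exercise.

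The facts in this stand: the power is unstated, Section 2.15 is silent on the extra 12 patients, and the verb is wrong for an assumed arm difference. The inference that a stated commitment was missed does not stand. The 80% sentence in Section 2.15 does not tie the final size to the 60-patient result, and both calculations in Section 3.1 use 80%. The 60 patients are contained in the 72, and the SAP gives its reason for using the larger set. Anyone reading Section 3.1 can see that 164 falls short of one requirement and exceeds the other.

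On the wording, the same paragraph opens by calling the calculation blinded, and Section 2.15 does too. One loose verb is weak evidence against that. Nor could a reviewer supply the replacement: writing that 4.352 was assumed from the pooled mean would assert a derivation that the SAP does not give.

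**Conclusion.** No change to the plan follows. The target of 164 is an openly described compromise between two re-estimates. Unadjusted H1 power is about 74-76% under the less complete estimate and 87-88% under the fuller one, using the SAP's SDs, one-sided 5% and 78 to 82 evaluable patients per arm. Whether the shortfall under the 60-patient estimate survives covariate adjustment is unresolved; a correlation of about 0.3 to 0.4 would remove it.

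The missing power statement is a gap in reporting, which the reader can fill from figures already in Section 3.1. The description of 4.352 is best read as a slip of wording, on the assumption that the re-estimation was blinded, as the SAP says. It is reported as already done. Recording its power and rewording a verb would leave the target, alpha, model, enrolment and every analysis result as they are.
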